#### 7.6 Reporting Procedures

#### Ambulatory Activity - Accelerometer (Visit 0 to visit 5)

Participants will be given an accelerometer at visit 0 and asked to wear the accelerometer for the whole study duration (Visit 0 to visit 5). The first eight days ahead of undertaking visit 1 (initiation of first treatment period) will measure habitual physical activity. The accelerometer will record sleep duration and quality, overall daily physical activity volume, time spent sedentary and time spent in light and moderate to vigorous physical activities (MVPA). Data will be used to assess habitual lifestyle behaviours and to assess compliance with exercise restrictions (no MVPA) prior to each clinical visit. Participants will also be asked to complete a wake and sleep log during the study. If participants remove the accelerometer, they will be asked to document the time that they removed it, the reason for it and when they re-attached it. An appropriately trained individual will instruct on correct placement of the monitor using the normal operating procedures. Participants will be given a stamped addressed envelope to return the accelerometer via post after the end of the second treatment period (if they prefer not to attend visit 5 in order to bring the accelerometer personally to Leicester Diabetes Centre). Data will be processed using an open source R programme (GGIR) according to SOPs developed for the NIHR Leicester Biomedical Research Centre.

#### **Questionnaire Data**

**Satiety and Hunger VAS score** - these scores will assess the feeling of satiety and hunger during the MMTT test at visits 2 and 4 [before initiation of the MMTT and 15', 30', 60', 90', 120', 150' and 180'

after consumption of the last mouthful of the meal)]. This will be completed at the time points above once blood samples have been drawn.

Additionally, at Visit 0 participant's self-reported physical activity level will be assessed using the International Physical Activity Questionnaire Short Form (IPAQ-SF).

#### Diet (food and drink)

Dietary intake and compliance with the standardised meals, along with times of food and drink consumption will be self-reported via a 3-day diet diary recorded over the two treatment periods. Pseudonymised data will be entered into a specialist dietary analysis software package (Nutritics). Intake will be analysed for total daily energy intake and macronutrient composition (carbohydrate, fat and protein). Compliance to standardised meals will be monitored and non-compliance recorded.

#### Episodes of hypoglycaemia during visits and daily life

All participants will be provided with a glucose monitor and a glucose monitoring diary during the study in order to be able to check their capillary glucose levels in case they experience symptoms suggestive of HYPO. If participants lose their glucose monitor during the study, a replacement monitor will be provided to them by the study team. Details on how to manage symptomatic hypoglycaemia will also be provided to the patients at visit 0. Definition of hypoglycaemic episodes as well as the different categories of hypoglycaemia is described below at section 9.4. Patients will be asked to document in the glucose monitoring diary any symptoms suggestive of HYPO during their visits and daily life. Patients will be asked to check their capillary glucose levels at the time that they experience symptoms and to document these in their glucose monitoring diary with details of the time, the date, and symptoms they experience. Participants will be asked to treat HYPO episodes only if glucose levels <3.0 mmol/l. Participants that are diagnosed with HYPO during the study will be provided with a blood glucose meter to keep after completion of the study. In the event that they lose their glucose meter after the end of the study, they would be required to speak to their G.P in order to recommend or replace it with a new one. Participants diagnosed with PHH will also be provided with an information leaflet on how to modify their diet at the end of the study. If symptoms of PHH are not improving with diet modifications, participants will be asked to consult their G.P on treatment options available to them to manage their symptoms.

#### Biochemical analysis – Blood Samples (screening, visits 2 and 4)

All laboratory results of blood tests performed during the study will be reviewed and the reports signed by the Investigator (or an individual/ individuals approved by the CI as listed on the delegation of authority log) who will record in the CRF whether they are normal, abnormal but not clinically significant, or abnormal. If abnormal a letter will be sent to the GP.

#### Laboratory Tests/ biochemical analysis (screening, visits 2 and 4)

Blood for measurement of FBC, renal function, liver function and HbA1C will be obtained at screening visit and will be analysed in UHL accredited laboratories and destroyed once analysed in accordance with the UHL's SOPs.

Blood for the measurement of glucose, insulin, and plasma for future analysis of appetite biomarkers (if consent is obtained for appetite biomarkers measurement from participant) will be obtained in fasting condition, immediately before and immediately after the intervention and during the 3-h standardised MMTT at 8 time points during each visit [at baseline (immediately before the standardised MMTT), at 15 minutes post-MMTT and then at 30 minutes, 60 minutes, 90 minutes, 120 minutes, 150 minutes and 180 minutes post-MMTT].

Blood glucose samples will be analysed in UHL accredited laboratories and destroyed once analysed in accordance with the UHL's SOPs. All laboratory results will be reviewed and the reports signed by the Investigator (or an individual/ individuals approved by the CI as listed on the delegation of authority log).

Blood samples for insulin will be collected into pre-cooled blood collection tubes containing EDTA (EDTA 4.9ml, 1 tube at each time point) to ensure sample viability. Blood collection tubes will be kept on ice prior to their use.

Once blood samples for insulin have been collected, they will immediately be spun in a refrigerated centrifuge (4°C) and the plasma will be obtained and aliquoted into eppendorf tubes. These eppendorf tubes will then be frozen (initially at -20°C but then transferred to -80°C on the same day as collection) until required for analysis. Samples for measurement of insulin will be analysed at Leicester General Hospital by the Research Scientists based at Leicester Diabetes Centre and then disposed of in accordance with the Human Tissue Authority's Code of Practice.

Following analysis, where a participant has consented, plasma samples will be stored indefinitely for future research use. A copy of the consent form will be retained for the duration of the sample's life to ensure that they will be used following the conditions that participants have given consent for.

#### **Exploratory endpoint**

The feasibility for the measurement of biomarkers of appetite (such as gut hormones) will be determined as new knowledge. Participants will have the option to consent to provision and storage of their samples for measurement of appetite hormones. If consent is given, additional samples will be obtained, these will be stored as plasma samples.

Blood samples for the majority of appetite hormones (if the participant has consented for these samples to take place) will be collected into pre-cooled blood collection tube pre-treated with 250ul of aprotinin (EDTA 4.9ml, 1 tube at each time point) at the same time points that blood sampling for insulin and glucose takes place. Moreover, at the same time points for blood collection for rest of appetite hormones, 2ml of blood will be collected with syringe and will be processed in accordance with the Leicester Diabetes Centre standard operating procedures for blood collection of samples for measurement of acylated ghrelin, a hunger hormone.

After each blood withdrawal the cannula will be flushed with saline to maintain patency. Blood samples will be centrifuged at the point of collection and the plasma will be obtained and aliquoted into eppendorf tubes. These eppendorf tubes will then be frozen (initially at -20°C but then transferred to -80°C on the same day as collection) until required for analysis.

#### 7.8 Randomisation

Randomisation will take place at the level of the individual using an independent online computerised randomisation service (sealed-envelope.com). Eligible participants will be randomly assigned at Visit 1 in a 1:1 ratio to the following treatment sequence:

Participants will be individually randomised (1:1) using a block design to one of the two trial sequences (below);

 Prolonged sitting for ≈6h 45min (control) followed by sitting [total ≈6h 15min] and one bout of AEX for 30min

or

Sitting (total ≈6h 15min) and one bout of AEX for 30 min followed by prolonged sitting for ≈6h
 45min (control).

Randomisation outcome will be revealed by a member of the study team. The independent researchers revealing randomisation allocation will sign the delegation of authority log and follow a local SOP to reveal the randomisation as requested.

Participants will be informed of their randomisation assignment during the Visit 1.

#### 7.9 Subsequent Assessments

After completion of visit 0 participants will be contacted and booked to attend visits 1 and 2 and visits 3 to 5 (Visit 1 at least 8 days post the screening visit [visit 0]). Randomisation will take place at Visit 1. After completion of the screening visit (Visit 0) the interventions (Visit 1 to 2 and Visits 3 to 5) will be undertaken over three consecutive days with a three day minimum washout period between them (visit 2 to 3) (maximum washout period will be 28 days). Ideally we would like a washout period to be 3-14 days in duration, however we allow a window of up to 28 days for the washout period (to allow flexibility, i.e. should participant require to self-isolate or household-isolate, etc.).

The outcome measures being collected at each visit are outlined in section 5.2 and listed in table 1. Any adverse events and changes from the screening/ baseline visit (e.g. medications) will be recorded. Due to the short nature of the trial, we anticipate few health related changes to be reported. At the start of the study, participants will be provided with a telephone number to contact the research team with any concerns.

#### 7.10 Definition of End of Trial

The end of the trial is defined as when the primary and secondary outcomes are all processed and analysed.

#### 7.11 Discontinuation/Withdrawal of Participants from Study Treatment

Each participant has the right to withdraw from the study at any time. In addition, the investigator (an individual/ individuals approved by the CI as listed on the delegation of authority log) may withdraw a participant from the study at any time if the investigator considers it necessary for any reason including:-

- Ineligibility (either arising during the study or retrospective having been overlooked/unknown at screening)
- An adverse event which requires discontinuation of the study or results in inability to continue to comply with study procedures
- Disease progression which requires discontinuation of the study or results in inability to continue to comply with study procedures
- Consent withdrawn
- Lost to follow up
- Subject deceased
- Loss of capacity
- Pregnancy
- Significant protocol deviation according to the judgement of the principal investigator
- Less than 16h 48min CGM data available for analysis over the 24-h period after intervention.

The reason for withdrawal will be recorded in the CRF and medical notes. If the participant is withdrawn due to an adverse event, the investigator will arrange for follow-up visits or telephone calls until the adverse event has resolved or stabilised. Use of identifiable data recorded or tissue collected up until the study withdrawal date will be used in analysis.

#### 7.12 Source Data

Source documents are original documents, data, and records from which participants' CRF data are obtained. These include, but are not limited to, hospital records (from which medical history and previous and concurrent medication may be summarised into the CRF and questionnaires). CRF entries will be considered source data if the CRF is the site of the original recording (e.g., there is no other written or electronic record of data). In this study the CRF and questionnaires will be used as

the source documents for the study. All documents will be stored safely in confidential conditions. On all study-specific documents, other than the signed consent form, the participant will be referred to by the study participant number/code, not by name.

#### 8. MANAGEMENT OF TRIAL PARTICIPANTS

#### 8.1 Description of Study Intervention

The description of interventions is outlined in section 5.

#### 8.2 Storage of Study Equipment or Related apparatus

The equipment and standardised meals will be stored in accordance with the Leicester Diabetes Center departmental standard operating procedures.

#### 8.3 Compliance with Study Treatment

Attendance throughout the study visits will be recorded and three diaries (3-day diet diary, glucose monitoring diary and wake and sleep log) will be provided along with objective monitoring methods to ensure compliance with suggested food intake and physical activity during the treatment periods. If significant non-compliance with protocol (according to the judgement of the PI) or significant amount of missing data for the primary outcome (for example less than 16h 48min CGM data available for analysis over the 24-h period after intervention), these participants may be excluded from part of the analysis or the whole analysis.

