#### 11. STATISTICS

#### 11.1 Description of Statistical Methods

A CONSORT study flow diagram will detail the movement of participants throughout the BariEX study. Baseline descriptive characteristics will be summarised, with continuous variables expressed as mean values (and standard deviations) or median values (with lower and upper quartiles) where appropriate, and binary and categorical variables expressed as number (percentage). Where CGM data is missing from a given trial, the corresponding data will be excluded from the other trial during the same time period at the second treatment. Participants with less than 16-hours 48min CGM data available for analysis over the 24-hour period after the intervention will be excluded from the complete cases analysis. The primary outcome of the study will be the difference in the time spent in HYPO (defined as glucose levels <3.0 mmol/l as measured by CGM) between the AEX and control intervention during the first 24-h post-intervention.

For outcomes related to the standardized MMTT (secondary outcomes), data from blood samples collected pre-MMTT at lunchtime (exactly before MMTT consumption) and 15, 30, 60, 90, 120, 150 and 180 minutes after MMTT consumption (last mouthful of MMTT) will be used to calculate time-averaged AUC (Area Under the Curve), using the trapezium rule. In instances of symptomatic hypoglycaemia during the MMTT(where blood collection for glucose, insulin and appetite biomarkers as well as VAS scores for satiety and hunger will be terminated early), these participants will be excluded from the analysis of secondary outcomes related to the MMTT. Missing data on insulin, glucose, appetite biomarkers and VAS scores for satiety and hunger within a completed MMTT will be imputed using a linear regression method as previously reported (35, 36), provided baseline/pre meal value and ≥50% of data points within the MMTT are available. The primary and secondary outcomes will be analysed using GEE (Generalised Estimating Equations) with an exchangeable correlation matrix, taking into account repeated measures across conditions. Outcome distribution will be assessed, with Gamma models used for positively skewed data. Identity and log link functions will be explored with Gamma models, with an identity link preferred (to aid interpretation of results) unless log link provides a substantially superior model fit.

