The primary and main secondary outcomes will be analysed using a complete case approach. A sensitivity analysis will also be conducted where individuals in whom rescue action for symptomatic hypoglycaemia during the first 24-h post-intervention was required will be excluded from the

analysis. A second sensitivity analysis will be performed using individuals with any CGM data (i.e. including those with CGM data available for analysis is <16hours 48mins for the first 24 hours post-intervention). A value of P<0.05 will be considered statistically significant for all analyses. Statistical analyses will be carried out using commercially available statistical programmes.

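### One CGM threshold carries three different consequences in 7.11, 8.3 and 11.1, and 8.3 leaves exclusions for non-compliance from the whole analysis to undated judgement

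*Protocol*

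**What the plan says.** Three sections of the Protocol act on the same CGM shortfall.

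- **7.11 (withdrawal).** The investigator "may withdraw a participant from the study at any time if the investigator considers it necessary", and the listed reasons include "Less than 16h 48min CGM data available for analysis over the 24-h period after intervention". The section ends: "Use of identifiable data recorded or tissue collected up until the study withdrawal date will be used in analysis".
- **8.3 (compliance).** Two triggers are named: significant non-compliance as judged by the principal investigator, and a significant amount of missing primary-outcome data, with the 16h 48min figure given only as an example. For either, "these participants may be excluded from part of the analysis or the whole analysis".
- **11.1 (statistical methods).** Participants below 16h 48min "will be excluded from the complete cases analysis", and the complete-case approach is the primary one. Then: "A second sensitivity analysis will be performed using individuals with any CGM data", which explicitly takes in those below the threshold. Section 11.1 also has a matching rule: "Where CGM data is missing from a given trial, the corresponding data will be excluded from the other trial during the same time period". It names no exclusion for non-compliance.

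**The concern.** Permission to withdraw, permission to exclude to an open extent, and a fixed exclusion from one analysis are different instructions for the same participant. The first affects conduct as well as analysis. A participant withdrawn after period 1 never supplies the second condition, so the any-data sensitivity analysis cannot use the pair that it was designed to recover.

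The non-compliance clause in 8.3 is a separate problem. Section 11.1 defines the primary set by CGM completeness alone, whereas 8.3 allows removal from every analysis by judgement, with no criteria and no time limit. Participants are told their sequence at Visit 1 (7.8), and exercise cannot be concealed from those who supervise it. With 18 recruited, and about 14 left if the planned 20% drop out, one or two exclusions made after results are visible could move the estimate.

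Finally, the threshold is meant to guarantee a minimum of usable data, but the matching rule deletes further time. The order of the two steps decides what is actually guaranteed.

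**Working it through.** **1. The threshold.** 16h 48min = 16.8 h, and 16.8/24 = 70%.

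**2. The rules side by side, for a participant below 16h 48min.**

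| Section | Force | Consequence |
|---|---|---|
| 7.11 | may | leaves the study; data to that date are used |
| 8.3 | may, as an example | leaves part or all of the analysis |
| 11.1 | will | leaves the complete-case analysis |
| 11.1, second sensitivity analysis | will | is included |

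The two rows from 11.1 fit together. The row from 7.11 fits neither of them well. A participant withdrawn before period 2 has that whole period missing. Under the matching rule the corresponding period-1 time is then deleted as well, so no matched data remain, although 7.11 says that the data collected will be used.

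**3. When this can happen.** CGM data upload at detachment (7.4). If Visits 1 to 5 fit within the 10-day sensor life, one sensor is worn throughout (5.1), so a shortfall is seen only after both periods. The period-1 yield can be known earlier if a second sensor is fitted at Visit 3 (5.1), or if the participant removes the sensor and posts it back after the first treatment period (section 7, Visit 5).

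**4. What a lost pair costs.** Inputs from 11.2: difference 18 min, SD 25 min, within-person correlation 0.6, two-sided 5%.

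- SD of the difference = 25 × √(2 × (1 − 0.6)) = 22.36 min.
- Reproducing the plan: the normal formula gives n = (22.36 × (1.960 + 0.842)/18)² = 12.1, so 13, and 13/0.8 = 16.25, so 17. The paired t needs 15 pairs, and 15/0.8 = 18.75, so 19. Fourteen pairs give 79.5%, and 14/0.8 = 17.5, so 18. The planned 18 is reproduced to within one or two.
- Paired-t power (noncentral t) by number of complete pairs:

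| Pairs | 18 | 17 | 16 | 15 | 14 | 13 | 12 |
|---|---|---|---|---|---|---|---|
| Power, % | 89.6 | 87.6 | 85.3 | 82.6 | 79.5 | 76.0 | 71.9 |

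The steps are 2.0, 2.3, 2.7, 3.1, 3.5 and 4.1 points.

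**5. Matched time.** Let each period hold *h* hours. The smallest possible overlap is 24 − 2 × (24 − *h*) = 2*h* − 24.

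- Threshold checked per period before matching: 2 × 16.8 − 24 = 9.6 h = 9h 36min, or 40% of the day. This needs both periods at exactly 70% and gaps that do not overlap at all. With independent gaps at 70%, the expected overlap is 0.7 × 0.7 × 24 = 11.8 h.
- Threshold checked after matching: the floor is 16.8 h = 16h 48min.
- At 20 h per period (7.4 anticipates more than 20 h): the worst case is 2 × 20 − 24 = 16 h.
- To guarantee 16.8 h matched from a per-period check, each period would need (24 + 16.8)/2 = 20.4 h.

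**The case against.** The other side has good points, and several stand.

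- Sections 7.11 and 8.3 are both permissive, so 11.1 can be taken as the operative rule, with removal from only part of the analysis in 8.3 consistent with it. That is a possible reconciliation, but the text does not make it. Nothing subordinates 7.11 or 8.3 to 11.1, and removal from the whole analysis is also allowed.
- A reader might infer that excluding participants from the primary analysis and restoring them in a sensitivity analysis is itself a contradiction. It is not; that structure is normal.
- A reader might infer that every sensor failure becomes a drop-out. The documents do not support this. Withdrawal is optional, and with a single sensor worn throughout the shortfall appears only when both periods are over.
- A reader might take 9h 36min as the protocol's actual floor. Section 11.1 states the matching deletion first and then tests the data available for analysis, which can equally be read as a check on matched time. Some detail of this kind could sit in an analysis plan that is not shown. The point is therefore an ambiguity and comes second.
- In 8.3 the principal investigator's judgement attaches to non-compliance, not to missing CGM data. That this person is unblinded is an inference from the open intervention. CGM blinding is explained in 7.4 by its effect on participants' diet, and the Protocol does not say who else sees the data or when.
- The plan already allows 20% drop-out, and the power figures describe attrition in general. They show what a lost pair is worth, not how many this wording will lose.

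**Conclusion.** The inconsistency holds and should be corrected. One data-yield threshold leads to possible withdrawal, optional exclusion of unstated extent, or mandatory exclusion from the primary analysis alone, and the first of these can defeat the second sensitivity analysis when a sensor comes off before period 2. The non-compliance clause in 8.3 conflicts with 11.1's definition of the primary set and leaves room for exclusions made with results in view.

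The size is moderate. On the assumptions of 11.2, each lost pair costs about 2 to 3 points of power between 18 and 14 pairs, and about 3.5 to 4 points below 14. The documents give no expected number of such losses. The possible bias from discretionary exclusions cannot be quantified from the documents.

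The matched-time point is conditional: 9h 36min at worst if the threshold is checked per period first, 16h 48min if it is checked afterwards. None of this shows that the sample size of 18 is wrong.

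**What to change.** - **7.11:** delete the CGM-yield bullet, so that a data shortfall alone does not end participation. All other withdrawal reasons stay as they are.
- **8.3:** for missing CGM data, refer to 11.1. For non-compliance, confine exclusions to a per-protocol sensitivity analysis, with the list of exclusions settled and dated before the CGM data are opened.
- **11.1:** state that 16h 48min applies to matched time, after the pairwise deletion.

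The cost is three short text edits. If the threshold would otherwise have been checked per period, a pair or two may move from the primary analysis to the any-data sensitivity analysis already planned. That carries the same power cost per pair as above, in return for a known minimum of comparable time in every pair analysed. Non-compliant participants with enough CGM data would remain in the primary analysis, and the per-protocol analysis would show how much they matter.
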